4.1.3 Cohort Specifications

Any cancer where the primary tumor is not clearly identified is not eligible for the cohorts described below (cohorts 1 to 9 and 11 to 16).

Cohort	Included histological types / subtypes and marker specifications	Excluded histological types / subtypes and excluded conditions
1 Cervical cancer	
 - squamous cell carcinoma - adenocarcinoma - adenosquamous carcinoma - non-squamous carcinoma of the cervix 	
 - small cell carcinoma - sarcomas - adenoid cystic carcinoma - adenoid basal carcinoma - undifferentiated carcinoma
2 Nasopharyngeal cancer	
 - non-keratinizing carcinoma - keratinizing squamous cell carcinoma - basaloid squamous cell carcinoma of the nasopharynx 	
 - nasopharyngeal papillary adenocarcinoma - salivary gland carcinomas - squamous cell carcinoma of the head and neck

Cohort	Included histological types / subtypes and marker specifications	Excluded histological types / subtypes and excluded conditions
3 MSI-H or MMR-deficient colorectal cancer	
 - adenocarcinoma of the colon (including cecum and sigmoid) or the rectum - MSI-H- or MMR-deficient tumor with details of results available prior to inclusion: 
 - tissue tested (tumor / non-tumor) - type of test performed - summary of all identified mutations 	
 - any histology other than adenocarcinoma - MSI or MMR test: 
 - no test performed - no test results provided - MSI low or MMR proficient
4 Known BRCA 1/2 mutated cancer 4a. Ovarian cancer 4b. Breast cancer	
4a. Epithelial ovarian, fallopian tube or primary peritoneal cancer
 
4b. Adenocarcinoma of the breast with BRCA 1 and/or BRCA 2 mutation
 
 - with details of results available prior to inclusion: 
 - type of test performed - summary of identified mutations 	
4a: Tumors of malignant mixed mesodermal or mucinous subtypes, or non-epithelial ovarian cancers (e.g. Brenner tumors, sex-cord tumors)
 
4b: Any histology other than adenocarcinoma
 
BRCA test: 
 - no BRCA mutation identified - no test performed - no test results provided 

5 Sarcoma 5a. Liposarcoma 5b. Leiomyosarcoma 5c. stromal tumor of the esophagus, stomach, small intestine, colon and rectum 5d. undifferentiated pleomorphic sarcoma 5e. Known translocation related sarcoma 5f. Radiation induced sarcoma 5g. Osteosarcoma 5h. Chondrosarcoma	
5a. Liposarcoma
 
5b. Leiomyosarcoma
 
5c. stromal tumor of the esophagus, stomach, small intestine, colon and rectum
 
5d. undifferentiated pleomorphic sarcoma
 
5e. any sarcoma type (including existing cohorts) with details of the following results available prior to inclusion: 
 - tissue tested and type of test performed - translocation detected 
 
5f. Any sarcoma type with a documented history of prior irradiation that includes: 
 - treatment with therapeutic irradiation at least 1 year prior to development of sarcoma - sarcoma arising within the field of previous therapeutic irradiation - differing histology between the sarcoma and the tumor that required radiotherapy 
 
5g. Osteosarcoma
 
5h. Chondrosarcoma
	
- all sarcoma types not explicitly listed in cohorts 5a to 5h
 
5c: Any location other than the esophagus, stomach, small intestine, colon and rectum
 
5e: Assessment of translocation: 
 - no translocation identified - chromosome abnormalities or mutations other than translocations - no test performed - no test results provided 
 
5f: No prior irradiation or irradiation within less than 3 years prior to study entry 
 - no tumor within the previously irradiated field or no clear record of the previously irradiated field - same histology as a prior tumor or no details on the histology of prior cancers 
 
5g: and 5h: Ewing sarcoma

Cohort	Included histological types / subtypes and marker specifications	Excluded histological types / subtypes and excluded conditions
6 Mesothelioma 6a. Pleural mesothelioma 6b. Peritoneal mesothelioma	6a. Pleural mesothelioma 6b. Peritoneal mesothelioma	Any location other than the pleura or the peritoneum
7 Cholangiocarcinoma /cancer of the biliary tract	Adenocarcinoma of the intrahepatic, perihilar, and distal extrahepatic bile ducts	Any tumor originating outside of the bile ducts Any histology other than adenocarcinoma
8 Thyroid cancer 8a. Anaplastic 8b. Differentiated 8c. Medullary and mixed medullary	8a. Anaplastic 8b. Follicular or papillary 8c. Medullary or mixed medullary and follicular or papillary carcinoma of the thyroid	- any location other than the thyroid - poorly differentiated thyroid carcinoma - and any other histology that is not a carcinoma
9 Gastric adenocarcinoma /adenocarcinoma of the gastro-esophageal junction (GEJ)	- adenocarcinoma of the - stomach - lower esophagus up to 5 cm above the GEJ	- squamous cell carcinoma and - any histology other than adenocarcinoma, - adenocarcinoma located in the esophagus more than 5 cm above the anatomic GEJ or in the duodenum
11 Malignant germ cell tumors	Specific to germ cell testicular tumors: - intratubular germ cell neoplasia, unclassified type - seminoma (including cases with syncytiotrophoblastic cells) - spermatocytic seminoma Specific to germ cell ovarian tumors - dysgerminoma Common histologies - embryonal carcinoma - yolk sac tumor - choriocarcinoma - teratoma (mature, immature, with malignant component) - tumors with more than one histological type	- epithelial tumors of the ovary and peritoneum - sex cord/gonadal stromal tumors, - carcinoma /adenocarcinoma, - trophoblastic tumors

Cohort	Included histological types / subtypes and marker specifications	Excluded histological types / subtypes and excluded conditions
12 ER+/HER2- breast cancer with high mutation load (>100 mutations) by local test	
 - adenocarcinoma of the breast - Mutational status 
 - > 100 mutations detected - summary of results (exact number of mutations) available prior to inclusion and report available upon request - type of test performed and location of tested tumor tissue - ER positive and HER2 negative with test results available prior to inclusion 	
 -any histology other than adenocarcinoma - assessment of mutational load 
 - mutations load ≤ 100 - no test performed -results of test not available - ER and HER2 test: 
 - ER negative and / or HER2 positive - no test performed - no test results provided
13 Thymoma and thymic cancer	13 a. all subtypes of thymoma 13 b. all subtypes of thymic carcinoma	
 - Lipoadenoma - Neuroendocrine epithelial tumors - any other tumor that is not a thymoma or thymic carcinoma
14 Gastroenteropancreatic (GEP) and lung neuroendocrine tumors (NETs) 14a. Low and intermediate grade (typical or atypical carcinoid) 14b. Poorly differentiated grade (excluding SCLC)	14 a. Carcinoid NET (atypical or not) of any GEP or lung locations 14 b. Poorly differentiated grade of any GEP or lung locations (excluding SCLC)	
 - Small cell carcinoma of the lung (SCLC) - locations other than gastroenteropancreatic or pulmonary
15 Known HPV induced squamous cell carcinoma	
Squamous cell carcinoma of:
 
 15 a. Oropharynx, oral cavity, hypopharynx, or larynx 15 b. Penis 15 c. Vagina or vulva 15 d. Anal canal 
 - with HPV16 detected on tumor tissue for oropharynx, oral cavity, hypopharynx or larynx or 
 with HPV16 or 18 detected on tumor tissue for penile, vaginal, vulvar and anal carcinomas - using ISH or PCR-based test - with details of test results (summary of identified serotypes) available prior to inclusion 	
 - Any non-squamous histology Depending on tumor types, this may include (without being limited to): 
 - adenocarcinomas, - sebaceous, clear cell, basal cell, small cell and undifferentiated carcinomas - 15a. tumor located in the nasopharynx or the salivary glands (any histology) - HPV test: 
 - No HPV detection on tumor tissue - HPV test not performed on tumor tissue - determination of HPV status not performed by ISH or PCR-based tests - no test results provided

Cohort	Included histological types / subtypes and marker specifications	Excluded histological types / subtypes and excluded conditions
16 Known MSI- high or MMR deficient solid tumors, excluding colorectal and gastric cancers	
 - any solid tumor that is not originating in the colon, the rectum, the stomach or the gastrointestinal junction - MSI-H- or MMR-deficient tumor with detailed test results available prior to inclusion: 
 - tissue tested (tumor / non-tumor) - type of test performed - summary of all identified mutations 	
 - any tumor originating in the colon, the rectum, the stomach or the gastrointestinal junction - MSI or MMR test: 
 - no test performed - no or incomplete test results - MSS or MMR proficient

The WHO Classification of Tumours will be used as a reference -
<http://publications.iarc.fr/Book-And-Report-Series/Who-Iarc-Classification-Of-Tumours>

For cohort 16, known MSI-H/MMR-deficiency will take precedence over histological subtype in patient cohort assignment.

If the Sponsor identifies that a patient has not been assigned to the right cohort, this patient can be re-assigned to the adequate cohort.

4.2 METHOD OF TREATMENT ASSIGNMENT AND BLINDING

This will be an open-label, unblinded trial. All patients will receive intravenous Atezolizumab at a fixed dose of 1200 mg q3w.

4.3 STUDY TREATMENT

4.3.1 Atezolizumab Formulation, Packaging, and Handling

The Atezolizumab drug product will be provided in a single-use, 20-cc USP/Ph. Eur. Type 1 glass vial as a colorless to slightly yellow, sterile, preservative-free clear liquid solution intended for IV administration. The vial is designed to deliver 20.0 mL (1200 mg) of Atezolizumab solution, but may contain more than the stated volume to enable delivery of the entire 20.0 mL volume. The Atezolizumab drug product is formulated as 60 mg/mL Atezolizumab in 20 mM histidine acetate, 120 mM sucrose, 0.04% polysorbate 20, pH 5.8.

Atezolizumab must be refrigerated at 2°C–8°C (36°F–46°F) upon receipt until use. Atezolizumab vials should not be used beyond the expiration date provided by the manufacturer. No preservative is used in the Atezolizumab drug product; therefore, each vial is intended for single use only. Vial contents should not be frozen or shaken and should be protected from direct sunlight.

For further details, see the Atezolizumab Pharmacy Manual and Investigator's Brochure.

4.3.2 Atezolizumab Dosage, Administration, and Compliance

The dose of Atezolizumab in this study will be 1200 mg administered by intravenous infusion every 3 weeks (21 [\pm 3] days).

Administration of Atezolizumab will be performed in a setting with emergency medical facilities and staff who are trained to monitor for and respond to medical emergencies.

Atezolizumab will be delivered in 250 mL 0.9% NaCl IV infusion bags with product contacting surfaces of polyvinyl chloride (PVC) or polyolefin (PO) and IV infusion lines with product contacting surfaces of PVC or polyethylene (PE) and 0.2 μ m in-line filters (filter membrane of polyethersulfone [PES]). No incompatibilities have been observed between Atezolizumab and these infusion materials (bags and infusion lines).

The initial dose of Atezolizumab will be delivered over 60 (\pm 15) minutes. If the first infusion is tolerated without infusion-associated adverse events, the second infusion may be delivered over 30 (\pm 10) minutes. If the 30-minute infusion is well tolerated, all subsequent infusions may be delivered over 30 (\pm 10) minutes.

For first infusion of study treatment, the patient's vital signs must be determined within 60 minutes before the infusion; during, and after the infusion if clinically indicated. For subsequent infusions, vital signs will be collected within 60 minutes before infusion and at the end of the infusion, if clinically indicated.

Patients will be informed about the possibility of delayed post-infusion symptoms and instructed to contact their study physician if they develop such symptoms.

No premedication will be allowed for the first dose of Atezolizumab. Premedication may be administered for Cycles \geq 2 at the discretion of the treating physician. The management of infusion-related reactions will be according to severity as follows:

- In the event that a patient experiences a mild (NCI CTCAE Grade 1) infusion-related event, the infusion rate should be reduced to half the rate being given at the time of event onset. Once the event has resolved, the investigator should wait for 30 minutes while delivering the infusion at the reduced rate. If tolerated, the infusion rate may then be increased to the original rate
- In the event that a patient experiences a moderate infusion-related event (NCI CTCAE Grade 2) or flushing, fever, or throat pain, the patient should have his or her infusion immediately interrupted and should receive aggressive symptomatic treatment. The infusion should be restarted only after the symptoms have adequately resolved to baseline grade. The infusion rate at restart should be half of the infusion rate that was in progress at the time of the onset of the infusion-related event
- For severe or life-threatening infusion-related events (NCI CTCAE Grade 3 or 4), the infusion should be stopped immediately, and aggressive resuscitation and supportive measures should be initiated. Patients experiencing severe or life-

threatening infusion-related events will not receive further infusion and will be further managed as clinically indicated until the event resolves

For anaphylaxis precautions, see [Appendix 4](#).

Guidelines for dosage modification, treatment interruption or discontinuation, and the management of specific adverse events are provided in Section 5.1.3 and the Atezolizumab Investigator's Brochure.

Any overdose or incorrect administration of study drug should be noted on the Study Drug Administration electronic Case Report Form (eCRF). AEs associated with an overdose or incorrect administration of study drug should be recorded on the Adverse Event eCRF.

Please refer to the Pharmacy Manual for detailed instructions on drug preparation, storage and administration.

4.3.3 Investigational Medicinal Product Accountability

All investigational medicinal products (IMPs) required for completion of this study (Atezolizumab) will be provided by the Sponsor where required by local health authority regulations. The study site will acknowledge receipt of IMPs using the IxRS to confirm the shipment condition and content. Any damaged shipments will be replaced.

IMPs will either be disposed of at the study site according to the study site's institutional standard operating procedure or returned to the Sponsor with the appropriate documentation. The site's method of IMP destruction must be agreed to by the Sponsor. The site must obtain written authorization from the Sponsor before any IMP is destroyed, and IMP destruction must be documented on the appropriate form.

Accurate records of all IMPs received at, dispensed from, returned to, and disposed of by the study site should be recorded on the Drug Inventory Log.

4.3.4 Post-Trial Access to Atezolizumab

The Sponsor will offer post-trial access to the study drug (Atezolizumab) free of charge to eligible patients in accordance with the Roche Global Policy on Continued Access to Investigational Medicinal Product, as outlined below.

A patient will be eligible to receive study drug after the end of the study if all of the following conditions are met:

- The patient has a life-threatening or severe medical condition and requires continued study drug treatment for his or her well-being
- There are no appropriate alternative treatments available to the patient
- The patient and his or her doctor comply with and satisfy any legal or regulatory requirements that apply to them

A patient will not be eligible to receive study drug after the end of the study if any of the following conditions are met:

- The study drug is commercially marketed in the patient's country and is reasonably accessible to the patient (e.g., is covered by the patient's insurance or wouldn't otherwise create a financial hardship for the patient)
- The Sponsor has discontinued development of the study drug or data suggest that the study drug is not effective for the cohort of advanced solid tumor into which the patient had enrolled
- The Sponsor has reasonable safety concerns regarding the study drug as treatment for the cohort of advanced solid tumor into which the patient had enrolled
- Provision of study drug is not permitted under the laws and regulations of the patient's country

The Roche Global Policy on Continued Access to Investigational Medicinal Product is available at the following Web site:

http://www.roche.com/policy_continued_access_to_investigational_medicines.pdf

Patients may also take part in an extension study if the patient is still benefiting from treatment (defined as no registered PD) at the time of planned Last Patient Last Visit date. If the extension study is not set-up in time for the patient to roll over by the planned protocol LPLV date, nor is there a Post-Trial Access Program available, the patient can continue treatment in the study until the extension study is opened at the patient's site. During the interim period between LPLV and a patient rolling over to the extension study, only safety data (AE including SAE and AESI) will continue to be collected in the eCRF. Other assessments (e.g. tumor assessment) can be performed as per standard of care.

4.4 CONCOMITANT THERAPY

4.4.1 Permitted Therapy

Concomitant therapy includes any prescription medications or over-the-counter preparations used by a patient between the 7 days preceding the screening evaluation and the treatment discontinuation visit.

Patients who experience infusion-associated symptoms may be treated symptomatically with acetaminophen, ibuprofen, diphenhydramine and/or famotidine or another H2 receptor antagonist, as per standard practice (for sites outside the United States, equivalent medications may be substituted per local practice). Serious infusion-associated events manifested by dyspnea, hypotension, wheezing, bronchospasm, tachycardia, reduced oxygen saturation or respiratory distress should be managed with supportive therapies as clinically indicated (e.g., supplemental oxygen and β 2-adrenergic agonists).

Systemic corticosteroids and tumor necrosis factor- α inhibitors may attenuate potential beneficial immunologic effects of treatment with Atezolizumab but may be administered at the discretion of the treating physician. If feasible, alternatives to corticosteroids should be considered. Premedication may be administered for Cycles ≥ 2 at the discretion of the treating physician after consultation with the Medical Monitor. The use of inhaled corticosteroids for COPD and mineralocorticoids (e.g., fludrocortisone) and low-dose corticosteroids for patients with orthostatic hypotension or adrenocortical insufficiency is allowed. Megestrol administered as an appetite stimulant is acceptable while the patient is enrolled in the study.

Colony-stimulating factors, such as granulocyte colony-stimulating factor and erythropoietin, should only be used according to the ASCO and ASCO/ASH guidelines, respectively ([Smith et al. 2006](#); [Rizzo et al. 2010](#)). Influenza vaccination should be given during influenza season only (approximately October to March). Patients must not receive live, attenuated influenza vaccine (e.g., FluMist®) within 4 weeks prior to Cycle 1, Day 1 or at any time during the study treatment, or within 5 months after the last dose of Atezolizumab, but may receive inactivated vaccine.

Patients who use hormonal therapy with gonadotropin-releasing hormone agonists or antagonists for prostate cancer, oral contraceptives, hormone-replacement therapy, prophylactic or therapeutic anticoagulation therapy (such as low molecular weight heparin or warfarin at a stable dose level), or other allowed maintenance therapy (see Section [4.1.2](#)) should continue their use.

Females of reproductive potential should use a highly effective means of contraception.

All concomitant medications should be reported to the investigator and recorded on the appropriate eCRF.

4.4.2 Prohibited Therapy

Any concomitant therapy intended for the treatment of cancer, whether health authority-approved or experimental, is prohibited. This includes but is not limited to the following:

- Chemotherapy, hormonal therapy, immunotherapy, radiotherapy, investigational agents or herbal therapy (except for maintenance therapies outlined in Section [4.1.1](#), and [4.1.2](#))
 - After Cycle 2, certain forms of radiotherapy may be considered for pain palliation if patients are deriving benefit (e.g., treatment of known bone metastases). Please contact the Medical Monitor prior to initiating radiotherapy.
 - Patients experiencing a mixed response requiring local therapy (e.g., surgery, stereotactic radiosurgery, radiotherapy, radiofrequency ablation) for control of three or fewer lesions may still be eligible to continue study treatment. Patients who receive local therapy directed at a target lesion will no longer be evaluable for radiographic response but will remain evaluable for progression. Such cases must be discussed with and approved by the Sponsor

- The concomitant use of herbal therapies is not recommended because their pharmacokinetics, safety profiles, and potential drug-drug interactions are generally unknown. However, their use for patients on study is allowed at the discretion of the investigator, provided that there are no known interactions with any study treatment. As noted above, herbal therapies intended for the treatment of cancer are prohibited
- Patients who are receiving a receptor activator of nuclear factor kappa B ligand inhibitor (denosumab) prior to enrollment must be willing and eligible to receive a bisphosphonate instead while on study; denosumab could potentially alter the activity and the safety of Atezolizumab

Patients should not receive any live, attenuated vaccine (e.g., FluMist®) at any time during the study while the patient is receiving Atezolizumab and for a period of 5 months after the discontinuation of Atezolizumab.

Patients are not allowed to receive immunostimulatory agents, including but not limited to interferon (IFN)- α , IFN- γ , or IL-2, during the entire study. These agents, in combination with Atezolizumab, could potentially increase the risk for autoimmune conditions.

Patients should also not receive immunosuppressive medications, including but not limited to cyclophosphamide, azathioprine, methotrexate, and thalidomide. These agents could potentially alter the activity and the safety of Atezolizumab. Systemic corticosteroids and anti-TNF- α agents may attenuate potential beneficial immunologic effects of treatment with Atezolizumab, but may be administered at the discretion of the treating physician. If feasible, alternatives to these agents should be considered.

In addition, all patients should not receive other immunostimulatory agents for 10 weeks after the last dose of Atezolizumab.

The above list of medications is not necessarily comprehensive. The investigator should consult the prescribing information for any concomitant medication and contact the Medical Monitor if questions arise regarding medications not listed above.

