4.4.3 Secondary Efficacy Endpoints

Non progression rate (NPR) at 24 weeks is defined as the percentage of patients with “CR”, “CR (imputed)”, “PR”, “PR (imputed)”, “SD” or “SD (imputed)” at 24 weeks.

Week 24 occurs at Study Day 169. Allowing 20 days either side of the exact Week 24 study day, assessments that occur between Study Day 149 and Study Day 189 (inclusive) will be considered as a Week 24 assessment.

Individual patient response at 24 weeks, based on RECIST v1.1, will be categorized as “CR”, “CR (imputed)”, “PR”, “PR (imputed)”, “SD”, “SD (imputed)”, “PD”, “Death in absence of PD”, “Discontinuation in absence of PD” or “Missing” as follows:

1. any patient who recorded PD at any post-baseline tumor assessment up to Study Day 189 inclusive, will be classified as “PD”,
2. any remaining patient who died at or prior to Study Day 189 will be classified as “Death in the absence of PD”,
3. any remaining patient will be classified as “CR”, “PR”, or “SD” according to their Investigator-reported tumor assessment data that falls within the window of Study Day 149 – 189 inclusive (taking the worst case if there are two conflicting assessments within the window),
4. for a patient who does not meet any of the above criteria, but who has a nearby later assessment (up to Day 209), the patient will be classified as “CR (imputed)”, “PR (imputed)” or “SD (imputed)” according to the first tumor assessment in the extended window.

5. any remaining patient will be classified as "Discontinuation in absence of PD" if they have an End of Study date prior to Study Day 189 or, otherwise, as "Missing/Out of window".

Best overall response (BOR), based on RECIST v1.1, for an individual patient, is defined as the best overall response obtained until progressive disease, death or lost to follow up, whichever is the first, as follows:

1. CR for a patient with an overall tumour response assessment of CR at two consecutive visits at least 28 days apart. If applicable, any tumour assessment within the 28 day period must also record CR.
2. PR for a patient with an overall tumour response assessment of PR or CR at two consecutive visits at least 28 days apart without being a CR. If applicable, any tumour assessment within the 28 day period must also record PR or CR.
3. SD, for a patient with an overall tumour response assessment of SD, PR, or CR at one or more visits at least 42 days after start of study treatment, but are not a confirmed CR or PR.

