4. PD, for a patient with an overall tumour response assessment of PD at any visit, and does not meet the criteria for a BOR of CR, PR or SD.
5. Missing, for a patient with an assessment of SD, PR or CR in the first 42 days after start of study treatment and no further tumour assessments thereafter.

Best overall response will summarize the proportion of patients with each best overall response.

Overall response rate (ORR) is defined as the proportion of patients with a BOR of CR or PR.

Clinical benefit rate (CBR) is defined as the proportion of patients with a BOR of CR, PR or SD.

Duration of response (DOR), based on RECIST v1.1, is defined as the time from the first occurrence of a documented objective response (CR or PR) to the time of progression or death from any cause, whichever occurs first. For patients who do not die or experience disease progression before the end of the study or who are lost to follow-up, duration of objective response will be censored at the day of the last tumor

assessment. Note: DOR will not be analysed if there are less than 4 patients available for the analysis.

Progression-free survival (PFS), based on RECIST v1.1, is defined as the time from the first day of study treatment to the first occurrence of disease progression or death from any cause, whichever occurs first. A patient without a PFS event will be censored at the time of the last evaluable tumor assessment or, for patients with no tumor assessment after the baseline visit, at the time of the first day of study treatment plus 1 day.

Time to progression (TTP), based on RECIST v1.1, is defined as time from the first day of study treatment to the first occurrence of progressive disease or death due to disease progression, whichever occurs first. Patients who have not progressed or died due to disease progression at the time of study completion or who are lost to follow-up will be censored at the date of the last evaluable tumor assessment or, for patients with no tumor assessment after the baseline visit, at the time of the first day of study treatment plus 1 day.

Overall survival (OS) is defined as the time from the first day of study treatment to death from any cause. Patients who are still alive at the time of analysis (clinical cut-off) and patients who are lost to follow-up will be censored at the last date they were known to be alive.

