4.4.4.2 Response and lesion assessments

A swimmer plot will be provided to illustrate the response assessments over time, and a spider plot will be presented to show the change in sum of target tumor diameters (SLD) over time. A waterfall plot will show best SLD change from baseline.

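### The SAP's response outputs have no cut at local therapy to a target lesion, although Protocol 4.4.2 ends response evaluability at that point

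*Protocol*

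**What the plan says.** Protocol 4.4.2 allows local treatment during the study for a patient with a mixed response. Such a patient, treated "for control of three or fewer lesions may still be eligible to continue study treatment", needs the Sponsor's approval. If a target lesion is treated, the rule is: "Patients who receive local therapy directed at a target lesion will no longer be evaluable for radiographic response but will remain evaluable for progression".

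The SAP defines the response outputs in 4.4.3 and 4.4.4.2:

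- BOR is the "best overall response obtained until progressive disease, death or lost to follow up, whichever is the first".
- "Overall response rate (ORR) is defined as the proportion of patients with a BOR of CR or PR". CBR is built from BOR in the same way, with SD added.
- DOR is the "time from the first occurrence of a documented objective response (CR or PR) to the time of progression or death".
- mBOR uses the same categories, but its window ends only at death or loss to follow-up.
- "A waterfall plot will show best SLD change from baseline". A spider plot shows the change in the sum of target diameters (SLD) over time.

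Local therapy appears in none of these definitions, nor anywhere else in the SAP.

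**The concern.** Resecting or ablating a target lesion can lower the sum of diameters whatever the drug does. A PR, or a large drop in the waterfall plot, can then reflect the procedure. The protocol guards against this by ending response evaluability at the procedure while keeping the patient in the assessment of progression. The SAP is the document that will be programmed, and it does not carry that rule over. A programmer who follows it as written would use every recorded assessment up to the stated end of the window. At stake are descriptive secondary results: response rates, tumour-shrinkage plots, and which patients enter the DOR analysis. In the response rates and plots, any error favours the drug.

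**Working it through.** The plan gives no figure on this point, so there is none to reproduce. The check compares the texts and then works out the effect of one patient.

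**Step 1. Are patients still assessed after local therapy?** Yes. Protocol 4.4.2 allows treatment to continue. The Schedule of Assessments (Protocol Appendix 1) keeps tumour assessments going every 6 weeks to week 24 and every 12 weeks after that, until loss of clinical benefit or another listed end. Later assessments will therefore reach the database.

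**Step 2. Where does each output stop?**

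| Output | End of window in the SAP | Cut at local therapy? |
|---|---|---|
| BOR | PD, death or loss to follow-up | No |
| ORR, CBR | Inherited from BOR | No |
| Start of DOR | First documented CR or PR | No |
| mBOR | Death or loss to follow-up (not PD) | No |
| Waterfall and spider plots | None stated | No |
| NPR at 18 and 24 weeks, PFS, TTP, end of DOR | Driven by progression or death | None needed: 4.4.2 keeps these patients evaluable for progression |

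**Step 3. Does another SAP rule catch these patients?** To be evaluable under SAP 4.1.3.1, a patient needs study drug, a baseline assessment and a post-baseline assessment. The BOR classes are CR, PR, SD, PD and Missing, with no not-evaluable class for assessments after a procedure.

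**Step 4. Who could be counted wrongly in ORR?** Only a patient who meets all of these conditions:

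- a target lesion was treated;
- there was no RECIST v1.1 PD beforehand, since PD closes the BOR window;
- there was no response confirmed beforehand, since that response is genuine;
- CR or PR was then recorded at two consecutive visits at least 28 days apart, with at least one of them after the procedure.

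This is a narrow group. mBOR and the waterfall plot are more exposed, because neither has a stated stop at PD.

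**Step 5. Size per patient.** With the patient kept in the denominator, one wrongly counted response adds 1/n to ORR: 1/25 = 4.0 points, or 1/12 = 8.3 points.

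To illustrate, take an assumed 4 recorded responders in 25, with exact (Clopper-Pearson) 95% intervals. The documents do not say how many such responses occur; 0 to 2 is assumed only to show the scale.

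| Post-procedure responses not counted | ORR | 95% CI |
|---|---|---|
| 0 | 4/25 = 16.0% | 4.5 to 36.1 |
| 1 | 3/25 = 12.0% | 2.5 to 31.2 |
| 2 | 2/25 = 8.0% | 1.0 to 26.0 |

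If the one patient were also dropped from the denominator, ORR would be 3/24 = 12.5% instead of 12.0%, so the denominator rule has to be stated. Going from 4 responders to 3 also crosses a SAP threshold: "DOR will not be analysed if there are less than 4 patients available for the analysis".

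**The case against.** The strongest reply is that this is silence and not contradiction. The SAP takes disease status as the investigator recorded it, and investigators are bound by 4.4.2. The Sponsor approves each case and so knows of it. The rule could be applied when the response is entered, before the SAP algorithm runs. It is true that the SAP errs by omission. A reader might infer that it expressly counts these responses; it does not say so. But neither document tells the investigator to enter not evaluable after local therapy. The rule in Protocol Appendix 3 on partly measured assessments concerns missing measurements, and an irradiated or ablated lesion may still be measured.

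A second reply is that SAP 4.1.3.1 removes patients whose deviation compromises the efficacy endpoint, as listed in the Protocol Deviation Plan. That plan is not among the documents, so it may help. An exclusion of this kind would reach DOR and the waterfall plot, which are shown only for the Efficacy Set. Three limits remain:

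- Sponsor-approved local therapy is not clearly a deviation.
- Exclusion would remove the whole patient, although 4.4.2 keeps that patient evaluable for progression.
- It would leave BOR and ORR in the Safety Set unchanged, and SAP 4.4 reports most efficacy analyses in both sets.

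A third reply is that many mixed responses are already PD under RECIST v1.1, which closes BOR. This stands, and it is why the effect on ORR is likely to be small.

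**Conclusion.** The gap is real but minor. Followed as written, the SAP departs from a stated protocol rule in secondary response outputs, and in response rates and shrinkage plots the departure can only favour the drug. The size is 4 points of ORR per wrongly counted patient at n = 25 and 8.3 points at n = 12, assuming the patient stays in the denominator. How many patients are affected is unknown and may be none.

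Three stronger readings are tempting, and the documents do not support them:

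- **That ORR is inflated by some definite amount.** No count of local procedures is given, and having a procedure is not the same as becoming a confirmed responder.
- **That DOR should be cut at the procedure.** These patients remain evaluable for progression, so a response confirmed earlier should be followed to progression or death. Only a response that starts after the procedure is in question, and no direction of bias in DOR has been shown.
- **That the primary endpoint is compromised.** NPR at 18 weeks depends on progression, and recording PR where SD would have been recorded leaves it unchanged. No reanalysis of NPR is needed.

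**What to change.** Add one rule to SAP 4.4.3 and refer to it in 4.4.4.2. It should say:

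- Assessments after the date of local therapy to a target lesion are not evaluable for BOR, mBOR, ORR, CBR, the start of DOR, or SLD change in the waterfall and spider plots.
- The same assessments still count for progression: NPR at 18 and 24 weeks, PFS, TTP and the end of DOR.
- A response confirmed before the procedure stands.
- The patient stays in the denominator.
- The data source for the procedure date and the lesion treated is named. The protocol describes eCRF recording of concomitant medications but names no field for local procedures on study, so this needs checking first.

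The cost is a short SAP amendment and a date cut in the programming. The procedure date and lesion must be captured if they are not already, and ORR may fall slightly.
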